### **Stage 3: In lab sleep study**

When the patient has fully acclimated to the device, at approximately 8 weeks, an in-lab PSG will be performed in the UM Sleep Disorders Laboratory in order to quantify the relief of obstruction (measured by AHI) while wearing the ssNPA. Sleep studies will include six EEG channels (F3-A2, F4-A1, C3-A2, C4-A1, O1-A2, O2-A1 of the 10-20 international electrode placement system), 2 electro-oculogram channels (right and left outer canthi), chin and bilateral anterior tibialis surface EMG, 2 EKG leads, nasal and oral airflow (thermocouples), nasal pressure through pediatric sensor cannulae, thoracic and abdominal excursion (inductance plethysmography), and finger oximetry with pulse waveform. All recordings will be made on digital equipment (Compumedics, Inc.) with which the investigators have extensive laboratory-wide clinical and research experience. End-tidal or transcutaneous CO2 will be monitored per the AASM guidelines for pediatric PSG [22]. A research coordinator and a physician will be on call by page during the studies. Nocturnal PSGs will be scored by a single, experienced technologist masked to subject identity. Borderline polysomnographic features will be arbitrated between the technician and [name], MD, pediatric sleep physician. Scoring for sleep stages, respiratory events, periodic leg movements, and arousals will follow standard criteria for children [22].

In addition, after the PSG results have been generated, a study team member will call the patient's parent or caregiver to inform them of the results. The parent or caregiver will then fill out a final questionnaire (10-point Final questionnaire; Appendix M) allowing them to share their perceptions of the device tolerability and acceptability. This questionnaire will be administered using a 10-point response scale and mean and standard deviation scores as well as the percentage of those reporting satisfactory or better will be assessed. During this assessment, open response feedback will also be obtained from families to determine if design changes are required specific to this population that may improve usability. In addition, at baseline and at the final visit, sleep questionnaires (including the Pediatric Sleep Questionnaire [23], OSA-18 [24] and the children's version of the Epworth Sleepiness Scale [25]) will be completed by caregivers along with the Pediatric Quality of Life instrument [26] and the Family Impact Questionnaire [27]. These items are anticipated to be utilized in the R33 phase and will be tested in the R61 phase to determine the level of subject burden.

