## **4.0 OBJECTIVES**

### **4.1 Primary Objective R61 phase**

1. Assess the tolerability, safety, comfort, ease of use, and ease of maintenance of the ssNPA in treating pediatric OSA

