Families will return to the clinic at weeks 2 and 4 to ensure optimal care and evaluate the device safety, tolerability, and acceptability. In between the clinic visits, regular contact will be made with families by the team, daily during the first week and weekly by the 2nd week (see Appendices H-K). During these calls, caregivers will report night to night witnessed apneas, improvement in daytime awareness, improvement in sleeping patterns of the patient, and any adverse events. Beside the two clinical visits at 2nd and 4th week, the number and frequency of extra visits will depend on: (1) the child's current threshold; and (2) how the child and family advance through each step of the desensitization protocol. The decision to hold on a particular step of the desensitization program will be based on whether the child's current level of anxiety or opposition is elevated. A recommendation to discontinue ssNPA treatment may be made if the child or family do not make progress with wearing the device in 2-4 weeks (depending on the number of visits during that time). Discontinuation of ssNPA therapy may occur after case consultation with other members of the study team to ensure that all strategies have been considered.

Evaluation of the device safety, tolerability, and acceptability will be assessed by a survey of patients and caregivers using a validated questionnaire with 10-point response scale (Appendix K). Mean and standard deviation scores as well as the percentage of those reporting satisfactory or better will be assessed. Device safety will be determined by adverse events

Table 3. Milestones for successful completion of the R61 phase

R61 Milestones	Goal (out of 5 subjects)
1. Device optimization and manufacturing in clean/sterile manner	100%
2. Parent report of ease of insertion; $\geq 5$ on Likert scale of 1-10	60% (3 of 5)
3. Child able to tolerate device in place	60% (3 of 5)
4. Child able to maintain device in place during sleep	60% (3 of 5)
5. Parent report of adherence based on diary	60% (3 of 5)
6. Comfort rating $\geq 6$ on Likert scale of 1-10	60% (3 of 5)

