**ssNPA Sleep Study****Today's date:****ssNPA User Feedback Questionnaire**

Thank you for participating in the ssNPA sleep study. Based on your experiences over the last couple of months, please let us know about you and your child's experience using the ssNPA:

1. Overall, please rate the ease of insertion of the ssNPA:

Extremely easy 1 2 3 4 5 6 7 8 9 10 Extremely difficult

2. Overall, please rate your child's comfort with the device:

Extremely uncomfortable 1 2 3 4 5 6 7 8 9 10 Extremely comfortable

3. Please rate your child's overall sleep quality:

Worse sleep 1 2 3 4 5 6 7 8 9 10 Improved sleep

4. Overall, please rate your child's behavior during the day after using the ssNPA:

Worse than normal 1 2 3 4 5 6 7 8 9 10 Better

5. Please rate how you think the ssNPA works for your child's sleep:

Not effective 1 2 3 4 5 6 7 8 9 10 Effective

6. How likely are you to use this device for your child?

Highly unlikely 1 2 3 4 5 6 7 8 9 10 Definitely

Please provide any comments or suggestions you have regarding the device:

---

---

---

---

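### In R61 the caregiver rates ease and comfort on the 10-point final questionnaire after hearing the sleep-study result, which leaves those ratings open to expectation bias

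*Combined protocol and SAP*

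**What the plan says.** All references are to the combined protocol and SAP.

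- **Order of events.** Section 9.2, Stage 3, has the study team phone the family once the PSG has been reported, "to inform them of the results. The parent or caregiver will then fill out a final questionnaire". The form is the 10-point final questionnaire in Appendix M. Its stated purpose is "allowing them to share their perceptions of the device tolerability and acceptability".
- **What the form asks.** Item 1 of Appendix M reads "Overall, please rate the ease of insertion of the ssNPA", and item 2 asks about the child's comfort. The other four items cover sleep quality, daytime behaviour, perceived effectiveness and likelihood of use. All six run from 1 to 10.
- **Role of these ratings.** Section 4.1 gives the R61 primary objective: "Assess the tolerability, safety, comfort, ease of use, and ease of maintenance of the ssNPA in treating pediatric OSA". Table 3 in section 9.2 is headed "Milestones for successful completion of the R61 phase". It includes "Parent report of ease of insertion; $\geq 5$ on Likert scale of 1-10" and "Comfort rating $\geq 6$ on Likert scale of 1-10", each with a goal of 3 of 5 children. Section 10.3.1 repeats the list with a comfort cut-off of 7. Section 9.4 starts R33 recruitment once R61 has been completed successfully.
- **Other forms.** The day-one, daily and weekly forms (Appendices I to K) rate ease and comfort from 1 to 5. Section 9.2, Stage 2, nevertheless describes Appendix K as having a 10-point scale.
- **Schedule.** The table in section 9.3 puts the device surveys, a clinic visit and the sleep study in the same Week 8 column and sets no order among them.

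**The concern.** Ease and comfort ratings should describe about eight weeks of handling and wearing the device at home. The apnea-hypopnea index (AHI) is a different kind of information, and the caregiver does not have it until the results call. A caregiver who has just heard that the AHI fell sharply, or did not fall, may rate the whole experience in that light. The rating would then mix acceptability with efficacy.

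The plan guards against this kind of influence elsewhere. In Stage 3 the PSG scorer is masked to the subject's identity, and section 11.5.2 limits who sees outcome data. Nothing similar protects the caregiver's rating, although the exposure comes only from the order of a phone call and a form.

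At stake are the Appendix M summaries themselves and, if Appendix M is the source, two milestones that count towards completing R61.

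**Working it through.** **1. The plan's own figures.** The pass rule reproduces: 3/5 = 60%. The 95% margin of error that section 10.2.1 gives for a mean 10-point rating with n = 5 also reproduces: t(0.975, 4 df)/√5 = 2.776/2.236 = 1.242, against the stated 1.24 SD. Neither figure allows for a systematic shift in the ratings.

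**2. Which form can supply the 1-10 milestones?** The printed items compare as follows.

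| Form | Scale as printed | Timing |
|---|---|---|
| Appendices I, J, K | 1-5 | Home use, before the PSG result |
| Appendix M | 1-10 | After the results call |

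A comfort score of 6 or 7 cannot occur on a 1-5 form. An ease cut-off of 5 on such a form would accept only the top category. As printed, Appendix M is therefore the only form that fits the cut-offs. This is an inference from scale length, because no section names the source.

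**3. How many milestones are affected?** Table 3 lists six. Manufacturing has a goal of 100%. Tolerating the device, keeping it in during sleep and diary adherence carry no 1-10 cut-off and can use data gathered before the PSG. That leaves two: ease and comfort.

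**4. Sensitivity to one family.** One child of five is 1/5 = 20 percentage points. One family crossing the cut-off turns 2/5 (40%, not met) into 3/5 (60%, met), or the reverse.

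**5. Chance of meeting a milestone.** Let p be the probability that a family's rating passes, with five independent families. Then

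P(at least 3 of 5) = 10p³(1−p)² + 5p⁴(1−p) + p⁵.

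For p = 0.4 this is 0.2304 + 0.0768 + 0.0102 = 0.317. The documents give neither p nor a disclosure effect, so the values of p are assumptions.

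| p | P(at least 3 of 5) |
|---|---|
| 0.3 | 0.163 |
| 0.4 | 0.317 |
| 0.5 | 0.500 |
| 0.6 | 0.683 |
| 0.7 | 0.837 |

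An assumed upward shift of 10, 20 or 30 points from p = 0.4 gives 0.500, 0.683 or 0.837. Over starting rates of 0.3 to 0.6 and shifts of 10 to 30 points, the chance of meeting the milestone changes by 0.15 to 0.52. A disappointing result would act the other way.

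**6. Direction.** On the comfort item 10 is the best score, so a favourable halo moves the rating towards passing. On the ease item as printed, 1 is extremely easy and 10 extremely difficult. The same halo would lower that score and move it away from a cut-off of 5 or more. Even for one child with one result, the two items could move in opposite directions relative to their cut-offs.

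**The case against.** The strongest reply is that the milestones need not come from Appendix M. Table 3 and the description of its Likert scoring sit in the Stage 2 text on home evaluation. That text names Appendix K as the 10-point tool for safety, tolerability and acceptability, and section 9.3 schedules tolerability surveys throughout home use. Appendix M is also an imperfect match: its ease item runs the wrong way for the cut-off, and it has no tolerability item, although section 10.2.1 mentions 10-point tolerability measures. This stands as far as it goes. The documents conflict on scale and source, and Appendix M is only the likely source. It does not remove the exposure, because Appendix M is still completed after disclosure and is summarised as acceptability data.

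A second reply is that caregivers are unblinded anyway and have watched snoring, apneas and restfulness for weeks, so the result may add little. That is a fair reason for not putting a size on the bias. But knowledge of treatment cannot be avoided, whereas knowledge of the AHI at the time of rating is created by the sequence.

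A third is that R61 is a five-child descriptive phase. That limits the weight of the point, but the same small number lets one rating decide a milestone.

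A reader might also infer that the R33 questionnaires share the problem. The documents do not show this. Section 9.2, Stage 3, places the sleep and quality-of-life battery at baseline and at the final visit, and section 9.4 places it at the end of each 8-week period. Neither sets an order relative to disclosure, and nothing clearly assigns Appendix M to R33.

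**Conclusion.** The point holds in a limited form. The plan explicitly has caregivers complete Appendix M after learning the PSG result, so its ease and comfort ratings are open to avoidable expectation bias. The size cannot be computed from the documents. The changes of 0.15 to 0.52 in the chance of meeting a milestone rest on assumed pass rates and assumed shifts.

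The link to the milestones rests on the forms as printed. If Appendix M is the source, two of the six milestones are exposed, and one family can flip either.

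It would be tempting to say that the decision to proceed to R33 is contaminated, or biased in a predictable direction. The documents do not support that. The milestone source is unnamed, four of the six milestones carry no 1-10 cut-off, and the direction depends on each child's result and on the reversed ease item. The R33 primary outcome is AHI response on PSG, which this form does not enter.

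**What to change.** In section 9.2, Stage 3, have the caregiver complete Appendix M at the Week 8 visit or on the PSG night, before any PSG result is disclosed, and make the results call afterwards. State in Table 3 and section 10.3.1 that this pre-disclosure rating is the source for the 1-10 ease and comfort milestones, and correct the description of Appendix K as a 10-point form. Changing the order without naming the source would leave half the point open. Two neighbouring points need settling in the same edit: the direction of the ease item, and the comfort cut-off (6 in Table 3, 7 in section 10.3.1).

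As a precaution only, since the documents set no order there, collect the final sleep and quality-of-life battery before disclosure too, along with the R33 batteries at Weeks 8 and 16.

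The cost is protocol wording. A Week 8 clinic visit is already scheduled, and section 11.3.1 has a parent staying overnight for the PSG, so no extra visit, form or child is needed. One drawback is that likelihood of use would be rated without knowledge of the result. That single item can be repeated after the call.

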### 9.3 Schedule of Events Table

	Screen	Day 0	Week 1-2	End of Week 2	Week 3-4	End of week 4	Weeks 5-8	At 8 th week (approx)
Informed Consent		X						
Medical Hx/Medication Hx	X							X
Vital Signs/Physical Assessment	X							X
Clinical Laboratory Tests (eg polysomnography)	X							X
Baseline questionnaires		X						
Device placement		X						
Parent training		X						
At home device use			X		X		X	
Device tolerability surveys			X		X		X	X
Clinic visit				X		X		X
Adverse events evaluation (through daily/weekly phone calls)			X		X		X	X
Sleep and QoL surveys		X						X
Overnight sleep study								X

### 9.4 R33 Phase – Randomization

After the R61 phase is successfully completed, for the R33 phase we will recruit 40 children with HUAO meeting the inclusion criteria of severe OSA (AHI>10 or >5 with hypoxemia) with the additional requirement that all subjects require the presence of at least one symptom of OSA (such as snoring 3 or more nights per week, daytime sleepiness, or hyperactive/inattentive behaviors). These latter symptoms will identify children at the highest risk for OSA and will minimize false positive from the baseline PSG. The exclusion criteria are the same as those delineated in the R61 phase clinical study.

Recruitment will occur from all clinics as well as community sources. In order to ensure that sufficient children complete the protocol and we have enough data from 40 subjects for our data analysis, we may recruit up to a total of 50 subjects to include for those children who may drop out before the end of 8 weeks study. All children will undergo a baseline PSG to determine eligibility and establish baseline data. All families will complete a questionnaire battery at the time of baseline PSG to acquire baseline measures. Eligible patients will be randomized 1:1 to receive (1) immediate therapy with the ssNPA device or (2) standard of care (SoC). The study will be designed as a randomized wait-list controlled clinical trial such that all children stand to benefit. Randomization will be stratified by baseline AHI scores (AHI>30 vs.  $\leq 30$ ).

At 8 weeks the ssNPA group will be able to continue the ssNPA for an additional 8 weeks while the SoC group will be offered the ssNPA for 8 weeks. At the end of the 8 week period, all children will undergo an in-laboratory PSG and repeat the questionnaire battery.

#### *9.4.1 Active group (ssNPA):*

Children randomized to the ssNPA device will have a device length sized and fitted by an otolaryngologist as described in the R61 phase. Families will be instructed on use of the ssNPA and an experienced nurse will assist each family with our desensitization protocol. Briefly, this will include an overview of the ssNPA and have the child and parent handle the device. If no child anxiety the parent will be requested to insert the ssNPA. A timetable will be agreed upon with dates when to move to the next step. Parents will be taught how to clean the device and will be educated and provided with handouts regarding safety and hygiene concerns. Children will be encouraged to use the ssNPA for 8 weeks, at which time a PSG will occur for primary outcome assessment. During these 8 weeks, regular contact will be made with families by the team to make sure they are comfortable with using the device. We will make daily contact during the first week of using the device and will continue during following weeks if needed. We will also ask parents/caregivers to send us a photo of the child wearing the ssNPA before parents go to bed and also in the morning. A sleep diary will also need to be filled out every day during these 8 weeks to report the child sleep and wake up time. After the 8-week PSG, the active group will continue wearing the ssNPA for another 8 weeks and have the final PSG at Week 16. The families will complete several validated assessment tools same as the baseline visit for comparison of subjective endpoints at the end of each 8-week period. Subjects and families will be notified that consent to participate is voluntary and can be withdrawn at any time.

#### *9.4.2 Waitlist Control Group; Standard of Care (SoC):*

Children randomized to the SoC will be treated based on the usual clinic standard of care for the initial 8 weeks after randomization. During the waiting time, they will continue to receive the treatment they would have had before which will likely include being placed on the waiting list for PAP. In our institution it is common for it to be six months from initial referral to PAP titration and approximately 8-10 weeks from the time of a baseline study to a PAP titration. As such, it is unlikely that the waitlisted children would receive PAP therapy clinically before the end of the proposed trial. During the 8 weeks waiting time, the control group will also be contacted by phone to maintain a connection with the team to minimize the chance for them to drop out. As with the active group, a PSG will occur 8 weeks after randomization for primary outcome assessment. At

Week 8, SoC group patients will also be offered the ssNPA device, and those who opt to receive the device will be fitted with the device to start using it for the following 8 weeks. Those who decline the ssNPA will continue with usual clinical care. If indicated, tracheostomy will be discussed at initial clinic visit and if a family prefers this intervention, it will be offered. However, our experience is a large majority of patients would rather elect palliative care. During the 8 weeks, the study team will be in regular contact with families as detailed above to make sure they are comfortable with using the device. All SoC group participants will then have the final PSG at Week 16.

The families in both active and SoC groups will complete several validated assessment tools same as the baseline visit for comparison of subjective endpoints at both 8 and at 16 weeks. Subjects and their families will be notified that consent to participate is voluntary and can be withdrawn at any time.

## **9.5 TREATMENT INTERRUPTIONS-DISCONTINUATION CRITERIA**

### ***9.5.1 Treatment Interruption Criteria***

In the event of patient illness, the patient will temporarily stop study treatment. Because nasal secretions and other upper respiratory symptoms can interfere with accurate data measurement and observation of treatment, the patient will have the option of pausing using the device until symptoms subside. Alternatively, if caregivers feel the device is providing symptomatic relief during the concurrent illness, they may continue use – however assessments, such as PSG will be postponed until resolution of acute illness to minimize artifact. Additionally, in the event of any temporary family emergency or necessary situation, the patient may also temporarily stop using the device. If for some reason there is a need for a different sized device, the treatment maybe paused while the new device is manufactured and delivered to the family. Observation will resume once the patient is treated with the new device.

The decision to hold on a particular step of the desensitization program will be based on whether the child's current level of anxiety or opposition is elevated. A recommendation to discontinue ssNPA treatment may be made if the child or family do not make progress with wearing the device in 2-4 weeks (depending on the number of visits during that time). Discontinuation of ssNPA therapy may occur after case consultation with other members of the study team to ensure that all strategies have been considered.

### ***9.5.2 Treatment Discontinuation Criteria***

#### **Patient willingness:**

During the study, the patient/caregiver has the right to withdraw from the study anytime. The study will provide consultations prior to study withdrawal to understand the issues that the patient encounters.

#### **Adverse events:**

Several design measures have been instituted to avoid device failure. If breakage of the ssNPA occurs, there would be the rare, theoretic possibility of airway foreign body. In addition, if there is a breakage or any additional severe adverse event observed in more than 2 patients and attributed to device design, the trial will also be terminated.

### **9.5.3 Clinical Trial Termination Criteria**

The Principal Investigator (PI), Data Safety Monitoring Board (DSMB), National Institutes of Health (NIH), and Institutional Review Board (IRB) officials reserves the right to terminate the clinical trial for safety or administrative reasons at any time.

Conditions that may warrant discontinuation of the trial may include, but are not limited to, the following:

- Discovery of an unexpected, serious or unacceptable risk to the patients enrolled in the study (that is likely related to the device) in greater than 1 patient.
- Decision on the part of the device manufacturer to suspend or discontinue testing, evaluation or development of the study product at any time.

